2.5.2.5 Birth Weight

The weight of the baby in kilograms was collected to two decimal places. If the participant gave birth to more than one baby, the weight of the lightest baby was used.

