2.9.5.1 Change to six months postpartum follow-up

Due to funding restrictions, data collection will end on 31/10/2020, and as a result it will not be possible to follow-up all participants to six months postpartum. Approximately 65% of women were followed up at six months postpartum as planned. The remaining 35% were followed up at less than six months postpartum by the TCC, as the follow-up period of the study was not long enough to follow-up these women at six months postpartum. Women who were followed up earlier than six month postpartum were contacted by the TCC between 01/08/2020 and 30/09/2020. Participants who could not be contacted by the TCC during this time period will be followed-up by research nurses up to 31/10/2020.

	Timepoint obtained/measured						
	Baseline	Follow-up 1: SSS Engagement	Follow-up 2: 4 weeks post quit date	Follow- up 3: 12 weeks post quit date	Follow-up 4: Late pregnancy (34-38 weeks gestation)	Delivery	Follow-up 5: 6 months post- partum
Age	х						
Height	х						
Weight	х						
Ethnicity	х						
English speaking	х						
Household income	x						
Deprivation quintile	x						
Quality of Life	х				х		х
Event dates	х	х	х	x	х	Х	х
Age first smoked	х						
Nicotine dependence level	х						
SSS attendance		x	х	х			
Self-reported smoking status	x		х	x	x		x

Table 3: CPIT III Data Collection Schedule

	Timepoint obtained/measured						
	Baseline	Follow-up 1: SSS Engagement	Follow-up 2: 4 weeks post quit date	Follow- up 3: 12 weeks post quit date	Follow-up 4: Late pregnancy (34-38 weeks gestation)	Delivery	Follow-up 5: 6 months post- partum
CO breath test result	х	х	х	x	х		х
Quit date		х					
Urine/saliva cotinine/ anabasine					x		x
Current E-cig use	х				x		x
Current NRT use	х	х			х		х
Expected date of delivery	х						
Actual date of delivery						х	
Multiple birth						х	
Birthweight						х	
Stillbirth/ Miscarriage		x	x	x	x	x	
Parity						Х	

3 Study Data

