4.5 Secondary outcome analyses

Engagement with SSS will be analysed using a mixed-effects logistic regression model adjusting for treatment group, age, years of smoking, income status, level of smoking (as measured by the Fagerström score) and whether the engagement data was collected before the 16th of March 2020, with centre as a random effect.

CO-validated smoking status at 4 weeks post-quit date will be analysed using a mixedeffects logistic regression model, adjusting for treatment group, age, years of smoking, income status, level of smoking (as measured by the Fagerström score) and whether the CO-validated smoking status was collected before the 16th of March 2020, with centre as a random effect. If a participant is missing their smoking status, it shall be assumed the participant is smoking.

Birth weight will be analysed using a mixed-effects linear regression model, adjusting for treatment group, the age, height and weight of the mother at booking, years of smoking, income status, level of smoking (as measured by the Fagerström score) and whether the birthweight data was collected before the 16th of March 2020 as fixed effects, and centre as a random effect. If a participant is missing data on birth weight, it shall be assumed the data is missing at random conditional on the covariates included in the analysis model [13, 14].

Continuous and point abstinence outcomes obtained at six months postpartum will be analysed using mixed-effects logistic regression adjusting for the same covariates and applying the same assumptions used in the primary outcome analysis (with the exception that whether the postpartum point abstinence outcome was collected before 16th of March 2020 will be adjusted for instead of adjusting for whether the primary outcome was collected before the 16th of March 2020). If a participant is missing their smoking status, it shall be assumed the participant is smoking. Participants who at postpartum were followed up earlier than 6 months will be excluded from the analysis of continuous and point abstinence

outcomes obtained at six months postpartum, and will be accounted for in a sensitivity analysis.

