4.8 Compliance with intervention

A CACE analysis for the outcome of birth weight will be used to obtain an unbiased estimate of the effect of the intervention with full compliance (defined as the participant being found to be a biochemically verified non-smoker at late pregnancy). An instrumental variable model will be used, using the compliance variable as the endogenous variable, and treatment group, the age, height and weight of the mother at booking, years of smoking, income status, level of smoking (as measured by the Fagerström score), whether the engagement data was collected before the 16th of March 2020, and centre as exogenous variables.

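### Birth weight uses the lightest baby of a multiple birth, but neither birth-weight model adjusts for multiplicity, which costs a little precision

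*SAP*

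**What the plan says.** Section 2.5.2.5 derives one weight per woman: "If the participant gave birth to more than one baby, the weight of the lightest baby was used".

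Section 4.5 sets out the model: "Birth weight will be analysed using a mixed-effects linear regression model, adjusting for treatment group, the age, height and weight of the mother at booking". The list continues with years of smoking, income status and Fagerström score, and closes with "whether the birthweight data was collected before the 16th of March 2020 as fixed effects, and centre as a random effect". It has no term for multiplicity.

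Section 4.8 uses the same outcome: "A CACE analysis for the outcome of birth weight will be used". Compliance is "defined as the participant being found to be a biochemically verified non-smoker at late pregnancy", and the instrumental variable model is specified by "using the compliance variable as the endogenous variable, and treatment group, the age, height and weight of the mother at booking", followed by smoking history, income status, Fagerström score, a Covid-period indicator and centre. Multiplicity is absent here too.

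Table 3 has a row "Multiple birth", collected at delivery. Section 2.7 says that randomisation was unstratified. The sensitivity analyses in section 4.7 include none restricted to singletons or adjusted for multiplicity, and the baseline shell (Table 4) has no row for it.

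**The concern.** The outcome combines two kinds of measurement: the weight of an only baby, and the smallest of two or more weights. Babies from multiple pregnancies can be expected to weigh less than singletons whatever the mother's smoking status, and taking the lightest widens the gap. Multiplicity is therefore likely to be a strong predictor of this outcome. The plan notices multiple births and writes a rule for them, but then leaves the variation they cause in the residual.

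Two things are at stake. First, the standard error is larger than it would be with a variable the trial already holds. Second, with only a handful of multiple births per arm, a visible imbalance could move a small estimate. Adjusting for it only after seeing that imbalance would look driven by the data.

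**Working it through.** **The plan's own figures.** The SAP gives no number for birth weight or multiple births. The two planning figures used here come from section 2.6: 470 per arm, and quit rates of 7% against 14%. They reproduce. With pooled variance, two-sided 5% and 90% power:

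n = [1.96 × √(2 × 0.105 × 0.895) + 1.2816 × √(0.07 × 0.93 + 0.14 × 0.86)]² / 0.07² ≈ 401 per arm.

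Allowing 15% loss, 401 / 0.85 ≈ 472 per arm, or 944 in total, against the stated 940.

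**Assumptions not in the SAP.**
- Multiple-birth rate p = 1% to 2%, which is 4.7 to 9.4 women per arm.
- Lightest-baby deficit d = 0.7 to 1.2 kg.
- Residual SD s = 0.5 to 0.6 kg.
- A birth weight for all 470 women per arm.

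**Shift from chance imbalance.** The SD of the between-arm difference in the multiple-birth proportion is √(2p(1−p)/470).
- p = 1%: 0.00649, or about 3.1 pregnancies.
- p = 2%: 0.00913, or about 4.3 pregnancies.

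Multiplying by d gives the one-SD shift in the arm difference:
- Low end: 0.00649 × 700 g = 4.5 g.
- High end: 0.00913 × 1,200 g = 11.0 g.

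Each extra multiple birth in one arm moves the difference by d/470, which is 1.5 to 2.6 g.

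**Standard error with and without the term.** With multiplicity in the model, SE = s√(2/470). Without it, SE = √{[s² + p(1−p)d²] × 2/470}.

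| p | d (kg) | s (kg) | SE with (g) | SE without (g) | Excess | Shift / SE without |
|---|---|---|---|---|---|---|
| 1% | 0.7 | 0.6 | 39.1 | 39.4 | 0.7% | 0.12 |
| 1% | 0.7 | 0.5 | 32.6 | 32.9 | 1.0% | 0.14 |
| 2% | 1.2 | 0.6 | 39.1 | 40.6 | 3.9% | 0.27 |
| 2% | 1.2 | 0.5 | 32.6 | 34.4 | 5.5% | 0.32 |

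**CACE.** To a first approximation, both the estimate and its standard error are the intention-to-treat values divided by the quit-rate difference, planned at 0.07 (a factor of 14.3).
- Shift: 4.5 / 0.07 ≈ 65 g to 11.0 / 0.07 ≈ 157 g.
- Standard error: 32.9 / 0.07 ≈ 470 g to 40.6 / 0.07 ≈ 581 g.

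The ratio of shift to standard error is unchanged at 0.12 to 0.32.

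**Validity.** This was checked in 20,000 simulated trials per scenario with no treatment effect and no other covariates.
- p = 1.5%, d = 1.0 kg, s = 0.55 kg: the unadjusted estimate averaged −0.3 g and the test rejected in 5.1% of trials. Adding the term cut the empirical SD of the estimate from 36.7 to 35.9 g.
- p = 2%, d = 1.2 kg, s = 0.5 kg: the average was 0.0 g and rejection 5.0%. The SD fell from 34.3 to 32.6 g.

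**The case against.** The strongest reply is that nothing in the plan is invalid. Randomisation balances multiplicity in expectation, stratified or not; what remains is sampling error, which the confidence interval already covers. The lightest-baby rule is explicit, gives one value per randomised woman and avoids clustering of babies within mothers. All of that stands.

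Two stronger readings are tempting, and the documents support neither. A reader might infer that an imbalance in multiple births biases the birth-weight effect, or is large beside it. If quitting added 200 g (an assumption), the expected arm difference would be 0.07 × 200 = 14 g, and a shift of 5–11 g looks large next to that. But the standard error of 33–41 g is more than twice 14 g with or without the term, so the standard error is the right comparator. A reader might also infer that the CACE makes matters worse. It does so in grams only, because the estimate and its standard error grow together.

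Two practical objections carry some weight. Table 3 records multiplicity at delivery, and the count then could differ from the count at randomisation if a fetus is lost in between. Also, section 2.8 says that the statistician is not blinded, and the amendment log dates version 1.1 to July 2021, after the end of data collection given in section 2.9.5.1 (31 October 2020). A late change to the covariates needs a clear record. Neither objection removes the case for the term.

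**Conclusion.** The point holds as a minor matter of precision and robustness. The plan leaves a strong predictor, which it already collects and which the intervention cannot change, out of both birth-weight analyses. The cost is a standard error about 1–5% larger than necessary, and an estimate that a few multiple births can move by about 0.1 to 0.3 of a standard error. Bias, false-positive rate and the primary outcome are not affected.

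The size rests on the assumed multiple-birth rate, weight deficit and SD, and on a birth weight being available for all 470 women per arm. The CACE figures in grams also depend on the quit-rate difference actually observed.

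**What to change.** - In section 4.5, add multiple pregnancy (yes/no) as a fixed effect in the birth-weight model.
- In section 4.8, add the same variable as an exogenous covariate in the CACE model.
- Report the number of multiple births by arm.
- In section 4.7, add a sensitivity analysis of birth weight in singleton births only.
- State that multiplicity, though recorded at delivery, is treated as fixed before randomisation, and why.
- Enter the change in the section 5 amendment log with its date and reason, because the statistician is unblinded.

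The lightest-baby rule can stay. The cost is SAP wording, one covariate and one extra analysis, with no new data.

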2.5.3 Adverse events

Serious adverse events (SAEs) that are related to the intervention will be documented. It is not anticipated that the provision of shopping vouchers to women will be associated with any related SAEs.

2.5.4 Other Collected Data

- *Demographics:* Maternal age, height and weight, household income and ethnicity were collected at baseline.
- Index of Multiple Deprivation (IMD) quintile: The IMD is a measure that ranks each lower layer super output area (LSOA) in order of deprivation, with the most deprived LSOA being ranked the highest. The IMD was derived for each participant by mapping to the participant's postcode. From the IMD the IMD quintile was then derived. A value of 1 represents the most deprived quintile, while 5 represents the least deprived. The postcode used to derive the IMD quintile was collected at baseline.
- The Fagerström Test for Nicotine Dependence (FTND): The FTND is used for assessing nicotine dependence. The test is composed of six questions, the scoring of which is detailed in Appendix 8.1. The FTND was collected at baseline.
- Other smoking information: The age at which the participant started smoking and whether the participant was currently living with someone who smokes were also collected at baseline, along with information on whether the participant used NRT and/or e-cigarettes.

- Antenatal appointment information: The date of the antenatal appointment and the CO reading taken as part of routine care (where available) were collected.
- *EQ-5D-5L:* The EQ-5D-5L was collected as a standardised measure of current health status developed by the EuroQol Group for clinical and economic appraisal. The EQ-5D-5L consists of five questions and a visual analogue scale, each assessing a different quality of life dimension (Mobility, Self-care, Usual activities, Pain/Discomfort and Anxiety/Depression). A weighted and population referenced summary index is derived and will be reported and analysed as part of the health economic analysis.
- Other birth data: Parity and the baby's birth date was collected as well as the status of baby at birth (live/stillbirth).
- Neonatal stay: For babies admitted to neonatal care, length of stay was recorded.
- *Miscarriage data:* Any known occurrence of miscarriage was collected throughout the study duration. The date the event became known to the trial team and date of miscarriage (where available) was collected.

2.6 Sample size

The aim was to recruit 940 participants to the trial (470 per arm). This gave 90% power to detect a doubling of the smoking cessation rate from 7% to 14%, allowing 15% loss to follow-up. The smoking cessation rate in the control group was derived from the smoking cessation rate found in the feasibility trial [2], and two other large trials of smoking cessation interventions in pregnant smokers [3, 4]. The smoking cessation rate in the intervention group was derived from the cessation rate in the feasibility trial, along with considerations of the effect size that would be considered clinically important.

2.7 Randomisation

Participants were allocated using a 1:1 allocation ratio to either intervention or control using random permuted blocks with randomly varying block sizes. No stratification factors were used when randomising the participants.

To try to prevent participants in the incentives arm using the timing of the primary outcome to 'game' the study and falsely obtain the final incentives voucher, all participants were randomly assigned a date for primary outcome follow-up between 34 and 38 weeks gestation, which was calculated using the participant's EDD.

2.8 Blinding

Due to the nature of the intervention, it was not possible to blind participants to treatment allocation in this pragmatic trial. In addition, due to the design of the trial, it was not possible for the statistician to be blinded to the treatment allocation. However, collection of self-reported smoking status at 34-38 weeks gestation was initiated blind to treatment allocation.

2.9 Follow-up

Follow-up of participants was undertaken at the engagement stage, 4 week post quit date, 12 week post quit date, 34-38 weeks gestation and six months post-partum (see section 2.9.5.1 for details of changes of the timing of the six months postpartum follow-up). A brief graphical outline of follow-up is given in Figure 1.

2.9.1 Follow-up 1: SSS Engagement

After the participant consented and was informed of group allocation, trial research staff contacted the participant's local SSS to ascertain if the participant attended a first appointment with an SSS advisor and set a quit date. This information was entered into the trial database for both control and intervention group participants. A £50 voucher was automatically dispatched to intervention group participants who attended and set a quit date.

2.9.2 Follow-up 2: Four weeks post quit date

For participants who engaged with the SSS and set a quit date, trial research staff contacted the participant's local SSS four weeks after this quit date to obtain smoking status in the last two weeks and CO breath test result as recorded by the SSS. Where a breath test result was not available from the SSS, trial research nurses collected this directly from the woman in the incentives group to initiate incentive payments. CO breath test results were collected for the control group only where these were available from the SSS in line with national SSS guidelines. This information was entered onto the trial database. If the CO result was at or below the accepted level for a non-smoker at the site, a £50 voucher was automatically dispatched to women in the incentives group.

2.9.3 Follow-up 3: 12 weeks post quit date

For participants in the intervention group who were confirmed quit at four weeks, trial research staff contacted the participant's local SSS eight weeks later to obtain smoking status and CO breath test result as recorded by the SSS. Where this was not available from the SSS, trial research nurses collected this directly from the participant. This information was entered into the trial database. If the CO result was at or below the accepted level for a non-smoker at the site, a £100 voucher was automatically dispatched.

2.9.4 Follow-up 4: Late pregnancy (34-38 weeks gestation)

All participants were followed up at the primary outcome stage in late pregnancy. Follow-up telephone contact was attempted by the trial contact centre at a random date between 34 and 38 weeks gestation allocated at the time of initial randomisation. Trial research nurses reviewed participants' notes one week prior to the telephone contact to check the health status of mother and baby and alert TCC staff to any adverse events e.g. miscarriage or stillbirth, that required particular sensitivity when conducting follow-up. TCC staff were blind to group allocation.

Three attempts were made by the TCC to contact women. If no contact was established, local research staff followed up women by telephone, text, and letter. On successful contact, women were asked: 'Have you smoked in the last 8 weeks?' If yes, 'Have you smoked more than 5 cigarettes in that time?'. EQ-5D-5L data, and current NRT/electronic cigarette use were also collected at this time point.

Self-report of not smoking was corroborated by cotinine estimation on saliva or urine (when saliva collection could not be tolerated). Where women were using NRT or e-cigarettes, anabasine assay on saliva was also conducted. Cotinine and anabasine were assayed by ABS Laboratories Limited (https://www.acmgloballab.com/about-us/our-locations/europe-london-uk). To minimise the potential for women to 'game' the primary outcome, incentive payments were dependent on the CO result, which is an immediate measure, and not on the cotinine or anabasine level.

An important aspect of the primary outcome for this phase III trial is the proportion of women successfully followed up in both the intervention and control group. To minimise loss to follow-up, particularly among controls, women in both groups will receive Love2Shop vouchers of £50 and £25 for providing data and saliva/urine samples where applicable at the primary (late pregnancy) and secondary (six months post-partum) outcome time points respectively (Figure 2.).

To assess if a) women lost to trial follow-up are still smoking towards the end of pregnancy, and b) the primary outcome has been 'gamed' (saliva cotinine below the cut-off but still smoking in late pregnancy) residual blood from routine late pregnancy samples, where available, will be tested.

2.9.5 Follow-up 5: Six months postpartum

Similar to the late pregnancy follow-up all women were contacted at six months after their expected delivery date to ascertain smoking status and collect a saliva/urine sample for those women who self-reported as quit. Quit status six months after birth was ascertained by two sets of questions:

1. 'Have you smoked in the last 8 weeks?' If yes 'Have you smoked more than 5 cigarettes in that time?', and 2. 'Have you smoked since your baby was born?' If yes, 'Have you smoked more than 5 cigarettes in total since your baby was born?'

Follow-up procedures (i.e. no. of contact attempts, data collection and saliva/urine sample collection and assay) were the same as those described for the late pregnancy follow-up. Biological samples of saliva and urine will not be available for use by other researchers.

2.9.5.1 Change to six months postpartum follow-up

Due to funding restrictions, data collection will end on 31/10/2020, and as a result it will not be possible to follow-up all participants to six months postpartum. Approximately 65% of women were followed up at six months postpartum as planned. The remaining 35% were followed up at less than six months postpartum by the TCC, as the follow-up period of the study was not long enough to follow-up these women at six months postpartum. Women who were followed up earlier than six month postpartum were contacted by the TCC between 01/08/2020 and 30/09/2020. Participants who could not be contacted by the TCC during this time period will be followed-up by research nurses up to 31/10/2020.

	Timepoint obtained/measured						
	Baseline	Follow-up 1: SSS Engagement	Follow-up 2: 4 weeks post quit date	Follow- up 3: 12 weeks post quit date	Follow-up 4: Late pregnancy (34-38 weeks gestation)	Delivery	Follow-up 5: 6 months post- partum
Age	х						
Height	х						
Weight	х						
Ethnicity	х						
English speaking	х						
Household income	x						
Deprivation quintile	x						
Quality of Life	х				х		х
Event dates	х	х	х	x	х	Х	х
Age first smoked	х						
Nicotine dependence level	х						
SSS attendance		x	х	х			
Self-reported smoking status	x		х	x	x		x

Table 3: CPIT III Data Collection Schedule

	Timepoint obtained/measured						
	Baseline	Follow-up 1: SSS Engagement	Follow-up 2: 4 weeks post quit date	Follow- up 3: 12 weeks post quit date	Follow-up 4: Late pregnancy (34-38 weeks gestation)	Delivery	Follow-up 5: 6 months post- partum
CO breath test result	х	х	х	x	х		х
Quit date		х					
Urine/saliva cotinine/ anabasine					x		x
Current E-cig use	х				x		x
Current NRT use	х	х			х		х
Expected date of delivery	х						
Actual date of delivery						х	
Multiple birth						х	
Birthweight						х	
Stillbirth/ Miscarriage		x	x	x	x	x	
Parity						Х	

3 Study Data

3.1 Trial Data

Data extracts without direct identifiers are passed to York Trials Unit from the Database Management Company using sFTP encryption in transit.

